#### **10 PRIOR AND CONCOMITANT MEDICATIONS**

All concomitant treatments documented during the study period will be summarized in frequency tabulations. Prior/concomitant medication coding will utilize the World Health Organization (WHO) Drug Dictionary

Any prior medications not considered prior anticancer medications will be listed along with concomitant medications. Prior medications will be defined as those medications with both a start and a stop date that is before the day of the first dose of study drug administration. If either the start date and/or the stop date of the medication is missing so that it is unclear

whether the medication was stopped prior to first dose of study drug administration then the medication will be included in the summary of the concomitant medications. Concomitant medications will be tabulated and summarized.

## **11 EFFICACY VARIABLES**

The following are the efficacy variables of interest:

## **11.1 Primary Efficacy Variable**

The primary efficacy variable is the investigator determined PFS per RECIST Version 1.1.

#### **11.2** Secondary Efficacy Variables

Secondary variables include:

- Objective Response Rate (ORR) according to RECIST Version 1.1
- Duration of Response (DR) according to RECIST Version 1.1
- Disease Control Rate (DCR)
- Overall Survival (OS)
- Change from baseline in PRO using the Functional Assessment of Cancer Therapy-Breast (FACT-B) questionnaire
- Treatment emergent AEs, laboratory abnormalities, physical examinations including vital signs and electrocardiogram (ECG) abnormalities
- Plasma PK parameters for lucitanib based on sparse sampling for POPPK analysis

## **12** EFFICACY ANALYSIS

#### **12.1** Primary Efficacy Analysis

Kaplan-Meier methodology will be used to summarize the time to event variables including the estimated 50th (median) percentile by treatment group.

#### 12.1.1 Progression Free Survival (PFS)

PFS is defined as 1+ the number of days from the date of first dose of study drug to disease progression or death due to any cause, whichever occurs first. Patients without a documented event of progression will be censored on the date of their last adequate tumor assessment (i.e., radiologic assessment), or the date of randomization if no tumor assessments have been performed. Progression events will be determined by the investigator.

#### 12.1.2 Objective Response Rate (ORR)

ORR is the proportion of patients with a best response of CR or PR according to RECIST Version 1.1. The best response is recorded from the start of treatment (Day 1) until disease

progression or recurrence. The ORR will be summarized with frequencies and percentages. The number and frequency of confirmed responses (CR+PR) will also be tabulated.

## **12.2** Key Secondary Efficacy Analyses

### 12.2.1 Duration of Response (DR)

DR for CR and PR will be measured from the date that any of these best responses is first recorded until the first date that PD is objectively documented. DR will be summarized using descriptive statistics (N, mean, standard deviation, median, minimum, and maximum).

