
Statistical Procedures
	
Analysis Populations
 
 • Efficacy population: all treated patients who received at least one dose of lucitanib and are confirmed as FGFR1- or 11q-amplified per the central laboratory • Safety population: all patients who have received at least one dose of lucitanib 
Sample Size Justification
 
Approximately 200 patients will be enrolled to the 10 mg and 15 mg daily dosing groups. A total of at least 80 patients in the 10 mg arm is sufficient to reliably estimate the median PFS and 6 month PFS rate in these heavily pre-treated patients. An observed median PFS greater than 4 months or similarly a 6-month PFS rate of at least 40% will be sufficient to consider the 10 mg dose group worthy of further study. Therefore, with at least 80 patients treated at 10 mg, the width of the 90% confidence interval for the 6 month PFS rate will be less than $\pm 10\%$ so that if the observed 6 month rate is 50% then the lower limit on the confidence interval will be greater than 40%.
 
Cohort C will enroll up to 40 patients to evaluate whether the PFS of a FGF non-amplified population is comparable to patients who are FGFR1- or 11q-amplified (Cohorts A and B).
 
The same target response of 40% will be used to evaluate Cohort C. With 40 patients, the width of the 90% confidence interval for the 6 month PFS rate will be less than $\pm 15\%$, so that if the observed 6 month rate is less than 25% then the upper limit on the confidence interval will be less than 40%, which is evidence that subsequent studies of 10 mg should exclude FGF non-amplified patients.
 
Statistical Methods
 
The Kaplan-Meier methodology will be used to summarize the primary endpoint of PFS. The 25th, 50th (median), and 75th percentiles will be presented along with the Kaplan-Meier estimates of the 6 and 12 month PFS rates.
 
The ORR and DCR will be summarized with frequencies and percentages. The DR and OS will be summarized utilizing Kaplan-Meier methodology.

Data Monitoring Committee
	
A data monitoring committee (DMC) consisting of two external investigator advisors and specified Clovis personnel will meet approximately quarterly after the first patient is enrolled to review the efficacy and safety data.
 
A detailed description of the composition, roles and responsibilities, and functioning of the DMC is provided in the DMC Charter.

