9.4 Two Monthly Follow-Up (All Cohorts)

- Survival status
- Subsequent therapies for breast cancer

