9.5.2 Efficacy Evaluations

9.5.2.1 Tumor Assessments

The first on-treatment scan should be completed on Cycle 2, Day 1, and every 8 ± 1 weeks through Cycle 6 (i.e., C4D1, C6D1). Thereafter, scans should be completed every 12 ± 1 weeks (i.e., C9D1, C12D1, C15D1, etc.) until disease progression. All patients must have scans to confirm radiographic progression. Tumor scans do not need to be repeated at end-of-study if <2 weeks since last scan or the patient had disease progression at the last scan. Patients that permanently discontinue lucitanib should continue scans until radiographic disease progression. Scans will be evaluated locally for patient treatment decisions. Copies of tumor scans will be

collected centrally to facilitate independent evaluation if subsequently required. Tumor response will be interpreted using RECIST Version 1.1 ([Appendix A](#)).

Tumor assessments should consist of clinical examination and CT scans of the chest, abdomen, and pelvis with intravenous contrast and appropriate slice thickness per RECIST Version 1.1; other alternative studies (MRI and X-ray) may be performed if clinically indicated. The same methods used to detect lesions at baseline are to be used to follow the same lesions throughout the clinical study.

Brain imaging is required at baseline. Patients with brain lesions detected at baseline require repeat brain imaging as part of the follow-up tumor assessments. The same methods used to detect brain lesions at baseline are to be used to follow the lesions throughout the clinical study.

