11.2.4.3 Duration of Response (DR)

DR for CR and PR will be measured from the date that any of these best responses is first recorded until the first date that PD is objectively documented. DR will be summarized utilizing Kaplan-Meier methodology.

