After the end of the treatment, the need for repetitive tumor evaluations depends on whether the trial has as a goal the response rate or the time to an event (progression/death). If ‘time to an event’ (e.g., time to progression, disease-free survival, PFS) is the main endpoint of the study, then routine scheduled re-evaluation of protocol specified sites of disease is warranted. In randomized comparative trials in particular, the scheduled assessments should be performed as identified on a calendar schedule (for example: every 6–8 weeks on treatment or every 3–4 months after treatment) and should not be affected by delays in therapy, drug holidays, or any other events that might lead to imbalance in a treatment arm in the timing of disease assessment.

Confirmatory Measurement/Duration of Response

Confirmation

As ORR is not the primary endpoint, confirmation of response is not required.

Duration of Overall Response

The duration of overall response is measured from the time measurement criteria are met for CR or PR (whichever is first recorded) until the first date that recurrent or PD is objectively documented (taking as reference for PD the smallest measurements recorded since the treatment started).

The duration of overall CR is measured from the time measurement criteria are first met for CR until the first date that recurrent disease is objectively documented.

Duration of Stable Disease

SD is measured from the start of the treatment (in randomized trials, from date of randomization) until the criteria for progression are met, taking as reference the smallest measurements recorded since the treatment started (if the baseline sum is the smallest, this is the reference for calculation of PD).

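### SAP 12.2.1 summarises duration of response with raw descriptive statistics where the protocol plans Kaplan-Meier, and has no rule for responders without documented progression

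*SAP*

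**What the plan says.** The protocol names Kaplan-Meier for DR in two places. The synopsis, under Statistical Procedures, says "The DR and OS will be summarized utilizing Kaplan-Meier methodology", and section 11.2.4.3 says "DR will be summarized utilizing Kaplan-Meier methodology".

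SAP section 12.2.1 keeps the protocol's definition of DR but changes the summary: "DR will be summarized using descriptive statistics (N, mean, standard deviation, median, minimum, and maximum". It does not mention that this departs from the protocol. SAP section 12.1, under the primary analysis, has a general sentence: "Kaplan-Meier methodology will be used to summarize the time to event variables". It does not name DR.

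The SAP has a censoring rule for PFS in section 12.1.1 ("Patients without a documented event of progression will be censored on the date of their last adequate tumor assessment") and one for OS in section 12.2.3 (last date known alive). DR has none in SAP 12.2.1, in protocol 11.2.4.3 or in protocol Appendix A, where the duration of overall response runs "until the first date that recurrent or PD is objectively documented".

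**The concern.** DR is a time-to-event variable whose only end point is documented PD. A responder who stops treatment for toxicity and then misses scans, withdraws consent, dies without PD, or is still responding when the study is stopped has no end date. Kaplan-Meier keeps such a responder at risk up to the last informative scan. A raw mean or median cannot. It has to omit the responder or put some other date (last follow-up, death, start of new therapy) in place of the end of response.

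Two analysts following SAP 12.2.1 could therefore report different DR values from the same data. Under independent censoring both omission and truncation pull the mean downward. If short responders are the ones lost and dropped, the error goes upward. The result would also not be comparable with the Kaplan-Meier DR that the protocol planned.

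**Working it through.** **1. Is the method really changed?** The list in SAP 12.2.1 (N, mean, SD, median, minimum, maximum) is the one SAP section 4 uses for ordinary quantitative variables, so its median is a sample median and not a Kaplan-Meier median. Where the SAP departs from the protocol on purpose it says so: section 5 states openly that the Efficacy Population is redefined. Nothing similar is said about DR.

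**2. Does another section fill the gap?** SAP 16.1 asks for the fullest use of the data and forbids imputation. The first speaks against dropping a responder without PD; the second speaks against treating last follow-up as the end of response. It does not settle the question.

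**3. Can such responders occur?** Protocol 9.5.2.1 limits their number: "Patients that permanently discontinue lucitanib should continue scans until radiographic disease progression". It cannot remove them:
- Treatment may end on clinical progression (protocol 5.1.2), and Appendix A says symptomatic deterioration is not an objective response category.
- Death without PD is a PFS event but does not end DR.
- The two-monthly follow-up in protocol 9.4 lists only survival status and "Subsequent therapies for breast cancer".
- SAP 2.2.3 ties trial completion to all patients being off drug and having had the end-of-study visit, not to PD.
- Protocol 13.6 allows early termination.

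**4. How large could the error be?** The documents state no precision figure for DR and no share p, so there is nothing to reproduce. The following is an illustration under assumptions.

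Inputs: DR D is exponential (assumed shape) with mean m = 7.6 months, the mean DR reported for the FGF-positive breast cohort in protocol 3.6.1.2. The true median is 7.6 × ln 2 = 5.27 months. Time to loss C is independent of D, and p = P(C < D).

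*Constant-rate loss.* If C is also exponential, then D given D ≤ C (responders without PD dropped) and min(D, C) (truncated at last follow-up) are both exponential with mean m(1 − p). Raw mean and median are therefore low by exactly the share p under either handling.

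| p | raw mean = 7.6(1 − p) | raw median = 5.27(1 − p) |
|---|---|---|
| 0 | 7.60 | 5.27 |
| 5% | 7.22 | 5.00 |
| 10% | 6.84 | 4.74 |
| 20% | 6.08 | 4.21 |
| 40% | 4.56 | 3.16 |

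Simulation with 1,000,000 draws per setting gave the same raw values at p = 10%, 20% and 40%, to within about 0.01 month. The Kaplan-Meier median stayed at about 5.3 months for every p tested from 10% to 50%.

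*Fixed cut-off 12 months after response.* p = exp(−12/7.6) = 0.206.
- Truncated mean = 7.6 × 0.794 = 6.03. The median is unchanged at 5.27 because the cut-off lies above it.
- Dropped mean = (7.6 × 0.794 − 12 × 0.206)/0.794 = 4.48.
- Dropped median = −7.6 × ln(1 − 0.794/2) = 3.84.

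*Uniform follow-up after response* (assumed ranges, 2,000,000 draws):

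| follow-up | p | dropped: mean / median | truncated: mean / median |
|---|---|---|---|
| 6–24 months | 17.4% | 5.13 / 4.05 | 6.28 / 5.26 |
| 3–12 months | 39.5% | 3.27 / 2.74 | 4.60 / 4.19 |

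*Informative loss, upward case.* Suppose 30% of responses shorter than 3 months are lost and dropped. P(D < 3) = 0.326 and E[D; D < 3] = 0.457, so 0.3 × 0.326 = 9.8% of responders are lost. The mean becomes (7.6 − 0.3 × 0.457)/(1 − 0.3 × 0.326) = 8.27 months, 9% too high.

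**The case against.** **SAP 12.1 might already cover DR.** The OS section of the SAP does not name Kaplan-Meier either, so OS gets its method only from the general sentence in 12.1. That sentence therefore reaches beyond the primary endpoint, and 12.2.1 could be read as adding descriptive statistics. This makes the SAP inconsistent with itself rather than silent. The specific DR sentence still reads most naturally as a replacement, and even on the generous reading there is no censoring rule.

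**Responders without PD should be few.** Scans are required until radiographic PD even after drug is stopped, survival follow-up continues until death or a sponsor decision (SAP 2.2.4), and the trial does not complete while anyone is still on drug. This stands. The cut-off scenarios above, including the 57% shortfall in the mean (3.27 against 7.6), would mainly arise from early termination or an early data cut. Under normal completion a small p, with an error of about 5–10% in the constant-loss model, is more plausible.

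**The 7.6-month anchor is weak.** It is a mean from a cohort with six breast-cancer partial responses, and the protocol does not say whether any were ongoing. It serves only as a scale. The proportional error under constant loss does not depend on it.

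**Dropping and truncating are not the only options.** A programmer could end DR at death or at new therapy, or list the response as ongoing. This is true, and it widens the range of results the SAP permits.

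**The consequence is limited.** DR is descriptive and secondary, and Kaplan-Meier on few responders is itself imprecise. This stands, and it bears on priority rather than on whether the text is wrong.

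**Conclusion.** The concern holds. SAP 12.2.1 departs without explanation from the method the protocol specifies twice, conflicts with the SAP's own general statement on time-to-event variables, and leaves undefined how a responder without documented PD contributes.

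Followed as written, it will generally give a distorted DR whenever such a responder exists. The size depends on p, which the documents do not give: nothing at p = 0, and a shortfall equal to p in both mean and median under exponential DR with constant independent loss. It can be larger if ongoing responses are cut off and dropped. The median may be untouched under truncation at a late cut-off, and the error is upward if short responders are selectively lost. All these figures rest on the assumed exponential shape and loss patterns.

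The effect is confined to DR, which the SAP lists under its key secondary efficacy analyses. Primary PFS and the criteria in SAP section 3 do not depend on it. It should be corrected before database lock but does not threaten the trial's main conclusion.

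**What to change.** Replace the last sentence of SAP 12.2.1 with:

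> DR will be summarized using Kaplan-Meier methodology. Responders without documented PD will be censored on the date of their last adequate tumor assessment. The Kaplan-Meier median with 95% CI will be presented, with the number of responders, PD events and censored responders.

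The SAP should say that the censoring rule is new because protocol 11.2.4.3 has none; it mirrors the SAP's PFS rule. Every responder has at least the scan that showed the response, so the censoring date always exists. The 95% level is a presentation choice. The quartiles and the 6- and 12-month rates listed in protocol 11.2.4 can be added.

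As a separate, explicit decision, state how death without PD is handled. Under the current definition it is not a DR event. Counting it as one would change the definition in protocol 11.2.4.3, Appendix A and SAP 12.2.1, so it should be labelled as such, for example as a sensitivity analysis. It would also help to state how new anticancer therapy before PD is treated, since the follow-up visits record it.

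The cost is a few SAP sentences before database lock and a run of the PFS Kaplan-Meier program on the responders. No new data are needed.

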## 12.2.2 Disease Control Rate (DCR)

The DCR is defined as the percentage of patients with a best response rate of CR, PR, or SD for at least 12 weeks. The DCR will be summarized with frequencies and percentages.

#### 12.2.3 Overall Survival (OS)

OS is defined as 1+ the number of days from the date of first dose of study drug to the date of death due to any cause. Patients without a documented date of death will be censored on the last date the patient was known to be alive.

#### 12.2.4 PK Sub Study (Cohort C)

Comparative PK parameters will include  $AUC_{0-t}$ ,  $C_{max}$ ,  $T_{max}$ ,  $T_{1/2}$ ,  $V_{SS}/F$ , and Cl/F for lucitanib and will be determined using noncompartmental methods.  $AUC_{0-t}$  will be calculated using the trapezoid rule. The PK parameters will be compared between the tablet and the capsule formulations.

## **13 POPULATION PK ANALYSES**

A specific POPPK data analysis plan will be developed and will outline the detailed approach to data handling, model development and diagnostics, individual model parameter estimation, exploration of covariate effects, and final model evaluation techniques. Results will be presented in a separate PK report to be appended to the clinical study report (CSR).

## **14 EXPLORATORY ANALYSES**

The exploratory endpoints will be summarized descriptively.

## **15 PATIENT REPORTED OUTCOMES**

PROs will be measured using the FACT-B questionnaire in all patients with both a baseline assessment and at least one post-baseline assessment.

The baseline PRO measurement will be defined as the last value prior to or on the day of the first dose of lucitanib. The on-treatment period will be defined as the day after the first dose of lucitanib to 28 days after the last dose of protocol-specified treatment. PRO measurements collected during the on-treatment period will be included in the summary tables.

The summary of PRO data will include descriptive statistics (N, mean, standard deviation, median, minimum, and maximum) of the maximum, minimum, and last value during the on-treatment period. Summaries using descriptive statistics of the change from baseline to the maximum, minimum, and last value during the on-treatment period will also be given by relevant cohort.

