^J Tumor scans obtained within 21 days prior to C1D1, may be used as the baseline scans. Scans should preferably be CT scans of the chest, abdomen, and pelvis with intravenous contrast and appropriate slice thickness per RECIST Version 1.1, using the same methods throughout the study that were used to detect lesions at baseline. Other alternative studies (MRI, X-ray) may be performed if clinically indicated. Brain imaging is required at baseline and must be repeated at follow-up tumor assessments for patients with brain lesions. The first on-treatment scan should be completed on C2D1, and every 8 \pm 1 weeks through Cycle 6 (i.e., C4D1, C6D1). Thereafter, scans should be completed every 12 \pm 1 weeks (i.e., C9D1, C12D1, C15D1, etc.) until disease progression. Tumor scans do not need to be repeated at End-of-Study if < 2 weeks since last scan or the patient had disease progression at the last scan. Scans will be evaluated locally for patient treatment decisions. Scans will be sent to a central radiological laboratory.

^K For patient selection, *FGFR1* and 11q amplification status may be determined based on local assessment, or based on central assessment as confirmed by a prescreening process. FFPE tumor tissue is required for all enrolled patients. The post-treatment biopsy is optional and requires additional consent. Detailed sample handling instructions are provided in the Laboratory Manual.

^L AEs will be assessed from the time of first dose of lucitanib through 28 days after the last dose.

^M On Day -7 a dose of the lucitanib tablet formulation will be given followed by a dose of the lucitanib capsule formulation on Day 1.

^N ECGs will be taken in triplicate anytime during screening, pre-dose (5–10 mins prior to dosing), and approximately 2 hr (± 5 min) post-dose on Day -7 (Cohort C) and Day 1 (All Cohorts) of each Cycle, and at End-of-Study, any time after treatment is discontinued.

^O LVEF will be assessed by ECHO or MUGA. It is recommended to use the same technique for a given patient throughout the study. ECHO should be performed at Screening, on C2D1, and every 8 weeks thereafter, and at the End-of-Study.

^P Whole blood will be collected pre-dose and processed locally for plasma ctDNA. Collections occur at screening, C1D1, C1D15, Day 1 of all subsequent Cycles, and End-of-Study. Refer to the Laboratory Manual for sample handling instructions.

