^Q Whole blood will be collected pre-dose and processed locally for plasma for PD biomarkers. Refer to the Laboratory Manual for sample handling instructions.

^R Plasma levels for sparse PK of lucitanib will be measured on pre-dose samples collected on C1D15 and Day 1 of Cycles 2, 3, and 5. An additional sample will be collected on C2D1, 1–3 hours post-dose.

^S Quality of Life Questionnaire (FACT-B) should be collected from the patient prior to dosing at C1D1; then on Day 1 of Cycles 3, 5, and 7. After Cycle 7, questionnaires will be collected every 3 cycles (on Day 1 Cycles 10, 13, 16, etc.), and at End-of-Study.

^T PK specimens will be collected at the following time points on Day -7 and Day 1: 5–10 min pre-dose, post-dose at 15 (± 2) min, 30 (± 3) min, 1 hr (± 5 min), 1.5 hr (± 5 min), 2.5 hr (± 10 min), 4 hr (± 15 min), 6 hr (± 15 min), 8 hr (± 15 min), 10 hr (± 30 min) (optional), and 24 hr (± 30 min).

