## 2.2.1 Screening Period

FGF-amplified (Cohort A) and FGF non-amplified (Cohort C) patients will undergo screening assessments within 28 days of the first dose of lucitanib.

Cohort A or C patients enrolled into the PK sub-study must undergo screening assessments within 21 days of the first dose of lucitanib, i.e., prior to Day –7.

For all patients, AEs will be assessed from the time of first dose of lucitanib through 28 days after the last protocol-specified treatment administration. Study-procedure-related AEs that occur after signing of the Informed Consent Form (ICF) and before administration of lucitanib will also be collected as AEs. AEs that occur after signing of the ICF and before lucitanib should be captured on the Medical History eCRF.

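### Read literally, the PRO baseline rule leaves PK sub-study patients without a FACT-B baseline: they are first dosed on Day -7 but first complete the questionnaire at C1D1

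*SAP*

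**What the plan says.** SAP 15 sets three rules for FACT-B, and Protocol 11.2.6 has the same text.

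- Baseline: "The baseline PRO measurement will be defined as the last value prior to or on the day of the first dose of lucitanib".
- Window: "The on-treatment period will be defined as the day after the first dose of lucitanib", running to 28 days after the last dose.
- Patients: FACT-B is taken "in all patients with both a baseline assessment and at least one post-baseline assessment".

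SAP 16.1 adds that missing data are not imputed.

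For the PK sub-study, Protocol Table 5 (footnote M) says: "On Day -7 a dose of the lucitanib tablet formulation will be given", with the capsule following on Day 1. Footnote S of the same table says of FACT-B that it "should be collected from the patient prior to dosing at C1D1". The questionnaire row of Table 5 is blank at screening and at Day -7. The procedure lists in Protocol 9.1 (screening) and 9.2.1 (Day -7) do not include FACT-B, and Protocol 9.5.8 starts the questionnaire on Day 1 of Cycle 1.

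**The concern.** The baseline rule and the PRO window are both tied to the first dose, while the questionnaire schedule is tied to C1D1. For most patients these are the same day. For PK sub-study patients they are at least a week apart, with the dose coming first, so no planned questionnaire can meet the baseline definition.

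Change from baseline in FACT-B is a named secondary endpoint. A group of patients who complete the questionnaire on schedule could contribute nothing to it, purely because of how the anchor date is worded. Participation is mandatory in Cohort C until the sub-study is full and optional in Cohort A, so the loss may not be spread evenly.

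**Working it through.** The documents give no PRO sample size to reproduce. The check applies the SAP date rules to the scheduled questionnaire days.

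**Inputs**

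- First dose: Day -7 in the PK sub-study (Table 5 footnote M; Protocol 9.2.1 and 9.5.5), Day 1 otherwise.
- That Day -7 counts as the first dose: SAP 2.2.1 says sub-study patients "must undergo screening assessments within 21 days of the first dose of lucitanib, i.e., prior to Day" -7. Protocol 5.1.1 says the same, and Protocol 9.1 places that 21-day window between Day -28 and Day -8.
- Gap between the two visits: at least 7 days (Table 5 footnote C; Protocol 9.5.5). No lucitanib is taken in between (Protocol 9.5.5).
- First four FACT-B days, with 28-day cycles: C1D1 = 1; C3D1 = 1 + 2×28 = 57; C5D1 = 1 + 4×28 = 113; C7D1 = 1 + 6×28 = 169.
- Sub-study size: up to 20, with additions allowed (Protocol 6.1; SAP 2.2.6). Total: up to 200 (SAP 3). Cohort A about 80; Cohort C up to 40.

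**Applying the rules**

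| | Baseline candidates (day ≤ first dose) | On-treatment (day > first dose) |
|---|---|---|
| PK sub-study, first dose Day -7 | none | 1, 57, 113, 169 |
| All other patients, first dose Day 1 | 1 | 57, 113, 169 |
| PK sub-study, anchored to C1D1 | 1 | 57, 113, 169 |

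In the first row, the requirement for a baseline removes the patient from the PRO summaries. If that requirement is not enforced, the C1D1 score enters the on-treatment maximum, minimum and last-value summaries, although a change from baseline still cannot be computed. These are alternatives: a patient removed from the tables has no C1D1 score in them.

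**Size, at the planned 20**

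- 20/200 = 10% of maximum enrolment.
- 20/(80 + 40) = 16.7% of the patients planned for Cohorts A and C.
- 20/40 = 50% of Cohort C, only if all 20 come from Cohort C.

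**How clean is a C1D1 baseline in these patients?** Protocol 3.6.1.1 gives a half-life of 31–40 hours. Seven days is 168 hours, so the fraction of the single dose remaining is 0.5^(168/31) = 2.3% to 0.5^(168/40) = 5.4%. FACT-B asks about the past 7 days (Protocol Appendix D), so with the minimum gap the recall period can reach back to the Day -7 dose.

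**The case against.** The strongest reply is that the first dose was meant to be C1D1, in which case nobody is lost. Several places support that reading:

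- Protocol 9.5.1.3 links the week after the first dose to the C1D4 visit.
- Protocol 9.5.1.2 times the pregnancy test from the first dose, while Table 5 footnote F times the same test from C1D1.
- Protocol 11.2.4.2 and SAP 12.1.2 equate the start of treatment with Day 1.
- Table 5 places Day -7 outside its daily-dosing columns.

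A programmer could anchor to C1D1 in good faith, and SAP 16.1 asks for data to be used as fully as possible. This stands as evidence that the documents are not uniform. It does not remove the problem. The three sections that address sub-study patients' first dose directly put it at Day -7, and the PRO rule says first dose, not C1D1.

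A reader might infer more than the documents support:

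- *That the patients drop out and their C1D1 score also counts as on-treatment.* Both follow from the definitions, but in the tables they are alternatives, as the working shows.
- *That half of Cohort C is lost.* Cohort A patients may also join the sub-study, so 50% is an upper bound.
- *That one reported group is known to be depleted.* SAP 4 presents all summaries by starting dose regardless of cohort, whereas SAP 15 gives PRO change by relevant cohort. Sub-study patients may have started at 10 mg or 15 mg depending on the amendment. The group affected cannot be identified.
- *That results are biased or efficacy conclusions affected.* The loss follows sub-study membership, not outcome, and no bias is shown. PFS, ORR and OS do not use this rule.

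**Conclusion.** The point holds. A stated rule, followed literally, gives PK sub-study patients no PRO baseline and excludes them from the FACT-B change-from-baseline summaries. This affects up to 20 patients as planned, at most 10% of 200, and more if the sub-study is enlarged.

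The conclusion assumes that Day -7 is the first dose, that no unscheduled FACT-B was completed on or before Day -7, and that the requirement for both assessments defines the analysis set. The count is a planned maximum; the documents do not give actual sub-study enrolment.

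The consequence is limited. The endpoint is secondary and descriptive, with no hypothesis or decision rule attached. It should still be corrected, because two programmers working from the same SAP could build different PRO datasets.

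**What to change.** In SAP 15 and Protocol 11.2.6, define PRO baseline for all patients as the last FACT-B on or before the day of C1D1, and start the PRO on-treatment period the day after C1D1. Scheduled patients without a baseline then fall from up to 20 to 0.

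The wording should be on or before the *day* of C1D1, not before the C1D1 *dose*. Otherwise a form completed on C1D1 after dosing, which the present rule accepts as baseline in patients outside the sub-study, would be neither baseline nor on-treatment.

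Add a table footnote that in PK sub-study patients this baseline follows one earlier single dose, which the 7-day recall period may reach.

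The cost is a sentence or two in each document and the footnote. No new data are needed, and the change can be made before database lock. The price is a baseline that is not strictly treatment-naive in these patients. Adding a FACT-B before the Day -7 dose would avoid that, but only for patients not yet enrolled.
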